R21 Protocol and Analysis Plan

Protocol #: 18-1138

Project Title: Pilot Evaluation of Hospice Decision Support Tools

Principal Investigator: [name]

Version Date: 01/08/19

I. Hypotheses and Specific Aims:

The goal of this project is to determine the feasibility and acceptability of a novel hospice patient decision aid (PtDA).

Aim 1: Determine the feasibility and acceptability of a hospice decision aid among a diverse population of older adults at multiple stages of illness and in two health care settings (an academic medical center and a county hospital system) using a mixed-methods approach.

Aim 2: Determine the preliminary efficacy of the hospice decision aid on decision quality, hospice knowledge, and values-concordance.

II. Background and Significance:

Although hospice has existed for more than 40 years, many people and even some physicians do not fully understand hospice care.¹ For example, many patients misunderstand the payment mechanism for hospice and incorrectly believe they are unable to afford hospice care, despite the fact that most payers cover hospice services. Some believe that enrolling in hospice requires institutionalization, despite evidence that 80% of hospice care occurs at home and those enrolled in hospice are more likely to die at home.¹⁻³ For some hospice conveys the message of “giving up”, even though evidence suggests that hospice enrollees and their loved ones report a sense of hope, relief, and improved quality of life.⁴⁻⁶ Finally, people report concerns that hospice hastens death, despite evidence that hospice is not associated with shorter survival and in some cases hospice enrollees live longer than those seeking curative treatments.^{5,7-10} To understand how to address these misconceptions, we performed a qualitative needs assessment with patients, caregivers and healthcare providers. We found, in addition to the aforementioned misunderstandings, that hospice is often not presented as an option until death is imminent and caregivers are consequently unaware of the potential support provided by hospice. Caregivers expressed regret for not knowing of and not enrolling in hospice earlier in the disease course of their loved ones. The patient decision aid (PtDA) being studied in this application is designed specifically to address these misperceptions of hospice care.

Hospice is underutilized. Despite the documented benefits of hospice, less than 2 million people utilize hospice services annually.² More than one third of all hospice users spend less than 7 days receiving care.² Approximately 40% of eligible Medicare beneficiaries die enrolled in hospice. In other words, almost two-thirds of eligible patients do not benefit from the documented advantages of hospice care. Racial and ethnic minority patients account for only 15% of all hospice users.^{2,11} When they are enrolled, they spend less time in hospice services than white patients, averaging fewer than seven days enrolled in hospice care.^{12,13} Further, the percentage of the oldest old utilizing hospice services has plateaued over the last several years with little more 50% enrolling in hospice.¹⁴ The reasons for underutilization are complex but include knowledge barriers and misunderstandings about hospice care by both physicians and patients,¹⁵⁻¹⁷ cultural beliefs about death,¹⁸⁻²⁰ lower health literacy in older adults and minorities,²¹⁻²³ physician gatekeeping and late referral,¹⁶ and disparities in access to quality healthcare.^{15,18,19,24}

The absence of quality shared decision making (SDM) and of quality patient-centered care is a disparity highlighted by the Institute of Medicine.²⁵ The goals of SDM include improved patient-provider communication, information sharing, and collaborative decision making.^{15,26,27} SDM is an important aspect of patient-centered care.²⁶ One strategy to support SDM is utilizing PtDAs which engage patients in the *process* of decision making by providing information on diagnosis and/or treatment options.^{28,29} PtDAs assume various forms including paper (e.g. leaflets, pamphlets, and booklets), electronic media (e.g. audio recordings, videos) and web-based interactive portals.³⁰ A Cochrane review of 115 randomized trials of PtDAs demonstrated a reduction of decisional conflict,

improved patient-provider communication, and increased patient involvement in medical decision making.³⁰ Video PtDAs are effective in older patients and patients with lower literacy and numeracy.³¹⁻³³ Critical to PtDAs is the presentation of balanced, evidence-based, accurate, neutral and unbiased information to patients.^{30,34}

III. Preliminary Studies/Progress Report:

We conducted and extensive qualitative needs assessment and environmental scan of available hospice decision aids. Though the needs assessment we interviewed 5 patients, 20 caregivers and 27 providers (e.g. social workers, nurses, chaplains) regarding their perceptions of participating in hospice. In the preliminary analyses, we found that all participant groups describe misunderstandings and myths regarding hospice care consistent with those cited in the literature. Additionally, we learned that timing of introduction and initiating of hospice care was a major theme across all participants. Hospice is often presented as an option only when death is imminent. As a result, caregivers expressed regret for not being aware of or enrolling their loved ones in hospice earlier in the disease course.

Our environmental scan found only 7 PtDAs that mentioned hospice as a potential secondary treatment option for people with illnesses such as end stage heart failure, cancer or kidney disease. The PtDAs did not describe the eligibility criteria hospice, the services provided by hospice and failed to provide resources for patients interested in hospice care. These PtDAs inadequately explain the nuances of hospice care as a primary treatment option and have limited reach to only specific populations. Further, these PtDAs fail to acknowledge the complexity of end-of-life decision making.³⁵

We then brought in 20 laypersons into our lab to conduct an organic web search for information regarding hospice and to participate in a semi-structured interview regarding their perceptions of the available information. Many of the online resources that the participants found were promotional materials from specific hospices or other special interest groups, thus the participants found these materials confusing and biased. Further, the online resources failed to provide clear information on cost, enrollment, and lacked the desired patient and caregiver testimonials. Surprisingly almost all participants went to sites such as yelp to get narrative descriptions of hospices.³⁵

IV. Research Methods

A. Outcome Measure(s):

Overview: The goal of the project is to determine the feasibility, acceptability and preliminary efficacy of a novel hospice decision aid. We will achieve this goal through a series of quantitative surveys and through qualitative methods.

Aim 1. Feasibility and Acceptability Outcomes:

Acceptability of the decision aid will be measured using the Ottawa Acceptability Scale (OAS). The OAS scale consists of 8 questions on a 5-point Likert scale with additional yes/no questions.³⁶ Feasibility will be assessed asking patients when they viewed the decision aid, if the used the paper version, the video version or both. We will also ask for input on the overall design and usefulness of the decision aid in facilitating their decisions.

Aim 2. Preliminary Efficacy:

Efficacy will be measured qualitatively and quantitatively through surveys. We are trying to determine if the decision aid improves hospice knowledge, decreases decisional conflict and improves self-efficacy.

- **Description of qualitative writing sample:** Hospice knowledge will be qualitatively assessed prior to randomization at the baseline visit to better understand the misconceptions associated with hospice care. Matsuyama et al³⁷ described a brief qualitative assessment in which participants are asked to describe “what is hospice” in their words. Participants will provide their answers on paper. These brief writings will be analyzed using thematic content analysis.

- **Knowledge of Hospice Test:** The Knowledge of Hospice Test is a 23-item scale with true/false questions.^{1,38} The Cronbach's alpha coefficient for the scale is 0.75 showing good internal reliability.
- **Decision Self-efficacy:** Is an 11-item instrument that one's self-confidence in decision making. This scale is a validated scale with a Cronbach's alpha of 0.92 and correlates with DCS subscale of being informed ($r=0.47$). Based on our prior study of a decision aid in palliative care, we hypothesize that one of the strongest effects of a decision aid might be to increase self-efficacy of the decision making.³¹

Hospice Beliefs and Attitude Scale (HBAS): The HBAS is an 8-item scale developed to measure beliefs and attitudes towards hospice care.³⁹ It has a Cronbach's $\alpha = .74$ for the scale, indicating a good degree of internal reliability.

B. Description of Population to be Enrolled:

Patients: Patients will be older adults age ≥ 65 with at least one life-limiting illness or syndrome as defined by the clinicians.

Exclusions: We will exclude patients who cannot speak English. In future work, we plan to make a Spanish version if this version is deemed acceptable. We will exclude patients with cognitive impairment as determined by ability to provide informed consent. We will also exclude patients on isolation precautions due to resistant bacteria or impaired immune function.

C. Study Design and Research Methods

Settings: For this pilot, we will recruit from Denver Health Medical Center and UCHealth. At each site, we will recruit patients from both the inpatient and outpatient palliative care services and the outpatient geriatric and primary care clinics. In order to get perspectives on feasibility of the PtDA in populations at different places in their illness trajectory. We plan to recruit 120 patients (**Figure 1**).

Hundreds of patients each year who meet our eligibility criteria are served in each setting, so we will have no difficulty recruiting 20-25 patients from each site/setting.

[figure not shown]

Figure 1. Recruitment

Recruitment: Patients will be identified differently in each setting:

- **In the outpatient setting,** potential patients will be identified through weekly chart reviews. The study team will communicate with the outpatient physician by his/her preferred communication method (e.g. email, phone) to determine whether the patients are appropriate to be approached. Reasons for non-approach will be recorded. If eligible and appropriate, a research team member will approach the patient and introduce the study following their clinical encounter.
- **In the inpatient settings,** the study team will speak with the palliative care teams twice a week to identify eligible patients who are currently being followed by the consult service. Then, a member of the study team will contact the attending physician of record for the patient to determine if he or she has concerns with the patient being approached regarding enrollment in the study. If eligible and appropriate, a research team member will approach the patient and introduce the study.

Research Methods: This will be a patient-level trial randomized in a 2:1 intervention: control (see figure 1 above).

- **Control - No PtDA:** Patients assigned to the control group will receive usual care. On the palliative care service, this typically includes a team with a physician, an advanced practice nurse, and occasionally other team member including a chaplain or a social worker. This consultation typically includes a discussion of advanced directives, symptoms, and prognosis. In the primary care settings, this is more variable and is a function of the primary care physician's practice and the patient's clinical situation.

- **Intervention - PtDA:** In addition to usual care, patients assigned to the intervention group will also be asked to view the hospice-PtDA. In the inpatient setting, the PtDA can be utilized anytime in the course of their hospitalization (all hospital rooms have a DVD player for the video). This could be before, during, or after the palliative care team consultation. In the outpatient setting, the patient will receive the PtDA after a clinic visit and will be allowed to take it home. In both settings, we have chosen a model with the PtDA delivery facilitated by research staff. The staff will NOT sit with patients while they watch the PtDA, as to allow patients to declare their desired use without study staff influence.

Data collection: For patients who agree to participate, the study coordinator will collect baseline demographic and quantitative data (surveys described above in Section A). The research coordinator will then open the envelope to determine the patient's allocation. Control patients will be asked to complete the baseline measures at time of enrollment and again at 1-month follow-up. Intervention patients will be given the decision aid and asked to review it within the next week. Then the best way to contact them 1 week later will be recorded (for outpatients, this will likely be at home by phone, for inpatients, this will likely be in the hospital.) Then the baseline surveys will be administered again by phone. Finally, each participant (control and intervention) will be contacted at one month for the final data point collection. \$25 gift cards will be given for baseline and one-month follow-up surveys.

- **Baseline visit (control & Intervention)-** All participants will be asked to complete the Hospice Knowledge Test, Decisional Conflict Scale, Decision Self-efficacy scale, SPMSQ, HADSA, PHQ-9 and demographics.
- **1 week Follow-up call (intervention only)-** Participants will be asked to complete the Hospice Knowledge Test, Decisional Conflict scale, Decision Self-efficacy scale and brief qualitative survey.
- **One Month Follow-up (control & intervention)-** At one month follow-up all participants will be asked to complete the Hospice Knowledge Test, Decisional Conflict scale and the Decision Self-efficacy scale.

D. Description, Risks and Justification of Procedures and Data Collection Tools:

The study team believes that this project poses minimal risk to all subjects involved. The intervention involves review of decisional support materials and a series of quantitative and qualitative questions. Data collection from participants includes questions and medical record review to screen for eligibility and only limited demographic data will be obtained. Audio-recordings of all qualitative will be kept on a secure server on the University network to which only the study to will have access. There is always a risk that participants may feel uncomfortable discussing hospice or end-of-life decisions. Participants will be informed of their right to refuse to answer any question they do not wish to answer, and may terminate participation in the study at any point (and that should they decline to participate, answer a question or withdraw this will not affect their medical care).

Data collection and storage has been planned to appropriately protect participant confidentiality. All patients will be given a unique identification number, and study data and identifiable information will always be kept separate. REDCap, the COMIRB-preferred system, will be used to store all survey and enrollment data, and the University's secure server will be used to store clinic audio files, interview audio files, transcripts and notes; access to both REDCap and the secure server will be limited to study personnel only. All paper documents will be stored in a secure and locked file cabinet in a secure and locked office building – again, all study data paperwork will be stored separate from paperwork with identifiable information (i.e. signed consent forms) and be accessible to study personnel only.

E. Data Analysis Plan:

Qualitative Data: The open-ended qualitative question will be analyzed using inductive and deductive content analysis.⁴⁰⁻⁴² The deductive approach will identify participant knowledge of key domains of hospice. The inductive approach will identify any key misconceptions or fallacies

expressed by participants in the study. The quantitative acceptability and feasibility measures will be analyzed descriptively with means and interquartile ranges. Analysis of qualitative data will be a continuous process beginning with initial interviews and continuing throughout and beyond the data generation period. All interviews will be audio-recorded and professionally transcribed verbatim. A multidisciplinary team, led by [name] will begin the analysis process with repeated readings of the transcripts to achieve immersion. The team will then develop and apply a list of codes to the transcripts using an emergent rather than a priori approach, in order to emphasize interviewee perspectives and de-emphasize team member speculations.^{43,44} All coded data will be entered into Atlas.ti v 7.0 (GmbH, Berlin) for data management. Coded transcripts will be analyzed within and across sites and settings to develop the major themes or concepts that the participants reported. The trustworthiness of study results will be enhanced through triangulation of the data and an audit trail throughout the data collection and analysis process. Following the interpretation of the qualitative findings, we will compare and contrast the results with the findings from the quantitative surveys using methods consistent with the NIH guidelines on mixed methods research.⁴⁵

Quantitative Data: We will compare differences between intervention and control using t-tests for continuous outcomes and chi-square tests for dichotomous outcomes. We will perform a multivariate analysis of our outcome variables (i.e. hospice knowledge, self-efficacy and decisional conflict) and look for mediation and/or moderation effects of age, race, and gender; while controlling for potential confounders. There is no power calculation as this is a pilot trial designed to test feasibility and acceptability.

G. Summarize Knowledge to be Gained:

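### The main between-arm comparison is an unadjusted t-test, and no planned analysis names baseline score, site or setting as a covariate

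*Combined protocol and SAP*

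**What the plan says.** **Sites, settings and size.** Section IV.C (Settings): "we will recruit from Denver Health Medical Center and UCHealth"; "We plan to recruit 120 patients"; "so we will have no difficulty recruiting 20-25 patients from each site/setting". Section G counts three settings: primary care, outpatient palliative care and inpatient palliative care. Section IV.C says they were chosen to reach patients at different stages of illness.

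**Allocation.** Section IV.C (Research Methods): "This will be a patient-level trial randomized in a 2:1 intervention: control". That sentence refers to Figure 1, which is not shown in the copy reviewed. Under Data collection, baseline data come first, and then "The research coordinator will then open the envelope to determine" which arm the patient is in. The text does not mention stratification, blocking or how the sequence is made.

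**Measurements.** The knowledge, decisional conflict and self-efficacy scales are completed by both arms at baseline and at one month. Only the intervention arm has the one-week call.

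**Analysis.** Section IV.E (Quantitative Data): "We will compare differences between intervention and control using t-tests for continuous outcomes", with chi-square tests for dichotomous outcomes. A multivariate analysis of the same three outcomes follows. It looks at age, race and gender as mediators or moderators and controls for confounders that are not listed. Site and setting are named only in the qualitative analysis.

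**The concern.** The protocol gives its own reason to expect setting to predict the outcomes. Section IV.C describes palliative consultation as usually covering advance directives, symptoms and prognosis, and describes primary care as more variable. Patients in different settings may therefore start with different knowledge of hospice and different confidence in deciding. A patient's own baseline score is also likely to predict the one-month score.

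A t-test uses none of this. With about 40 controls, precision is scarce, and a draw that puts too many patients from one setting in one arm shifts the estimate with nothing to correct it. Preliminary efficacy is Aim 2, and Section G makes a positive signal one condition for moving to a larger multi-site trial.

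**Working it through.** **Inputs from the protocol.** Two sites, three settings, 20–25 patients per site and setting, N = 120, ratio 2:1.

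**Assumptions.** The share of outcome variance lying between the six site-by-setting cells, ρ, is not given; I use 0 to 0.30. Tests are taken as two-sided at 0.05, which the plan does not state. Outcomes are in units of the total SD.

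**1. Planned size.** 2 × 3 × 20 = 120, which matches the plan. At 2:1 this is 80 and 40, with 40 patients per setting.

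**2. Chance imbalance if allocation is unstratified, with 80:40 fixed.** The number of controls X from a given setting is hypergeometric (120 patients, 40 in the setting, 40 drawn). The difference in shares is X/40 − (40 − X)/80.

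| Difference in one setting's share | A given setting | At least one of three |
|---|---|---|
| 10 points or more | 0.31 | 0.58 |
| 15 points or more | 0.10 | 0.22 |
| 20 points or more | 0.04 | 0.10 |

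A gap of 15 points or more means X ≤ 9 or X ≥ 18, against an expected 13.3. For example, 18/40 − 22/80 = 0.175.

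The unadjusted SE is √(1/80 + 1/40) = 0.194 SD. If one setting's mean differs from the others by 0.5 to 1.0 SD (assumed), a 15-point gap shifts the arm difference by 0.15 × 0.5 = 0.075 to 0.15 × 1.0 = 0.15 SD. That is 0.075/0.194 = 0.4 to 0.15/0.194 = 0.8 standard errors.

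**3. Validity of the t-test if allocation is unstratified.** Simulated trials with ρ from 0 to 0.30 gave an empirical SD of the difference of 0.192–0.195, a mean reported SE of 0.193–0.194, and type I error of 0.046–0.052. The between-setting variance is already in the residual, so the SE is correct.

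**4. Precision lost.** With adjustment and balanced cells the SE falls by √(1 − ρ). At ρ = 0.10 the unadjusted SE is 1/√0.90 = 1.05 times the adjusted one; at 0.25 it is 1/√0.75 = 1.15 times. In patients this is 120ρ = 12 to 30. Under unstratified allocation the net gain is smaller, because adjusting for chance imbalance has a price. The simulated SE falls from 0.193 to 0.187 at ρ = 0.10, about 3%, and from 0.194 to 0.177 at ρ = 0.20, about 9%. At ρ = 0 it rises from 0.193 to 0.198. These runs adjusted for six cells and did not include baseline score.

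**5. The t-test if allocation is within cells.** The true SE is √(1 − ρ) times the reported one, so type I error is 2[1 − Φ(1.96/√(1 − ρ))].
- ρ = 0.10: 1.96/0.949 = 2.07, giving 0.039 (simulated 0.037).
- ρ = 0.25: 1.96/0.866 = 2.26, giving 0.024 (simulated 0.025).

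**6. Baseline score.** If baseline and one-month scores correlate at r within arm, adjustment reduces the SE by a factor of about √(1 − r²). The documents do not give r, so I put no figure on this gain. It overlaps with the gain from setting wherever setting acts through the baseline score.

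**The case against.** The strongest defence has four parts.

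- **An adjusted analysis is already planned.** This is true, and it would be wrong to say that the plan stops at t-tests. But the confounders are left open. The sentence does not ensure that baseline score, site or setting enters the model, and it allows the list to be chosen after the data are seen.
- **Figure 1 may show allocation within cells.** This also stands. A reader might infer that the trial is unstratified; the documents do not establish that, because the text refers to a figure that is not available. The analysis point does not depend on the answer: one case costs precision and leaves imbalance in the main comparison, and the other makes the test conservative.
- **The t-test is valid.** Under unstratified patient-level allocation it is. A reader might infer that its standard errors leave out variation between settings and are therefore wrong. They do not leave it out, and the error rate is held. The SE is mis-stated, on the large side, only if allocation is stratified.
- **This is a pilot with no power calculation.** The main aims are feasibility and acceptability, which are analysed descriptively, and this point does not touch them. That limits the stakes. It is not a reason to use the less precise of two equally easy analyses for Aim 2.

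**Conclusion.** The point holds as one of precision and pre-specification. The stated between-arm comparison uses none of the baseline score, site or setting, and the supplementary analysis does not commit to them.

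Its size depends on two unknowns. If allocation is unstratified, a given setting is out of balance by 15 points or more with probability about 0.10. At an assumed cell share of 10–20% of outcome variance, adjusting for site and setting shortens the SE by about 3–9% net. If allocation is within cells, type I error is about 0.04 at an assumed 10% share and about 0.025 at 25%. The gain from baseline score comes on top, in part, and cannot be sized from the documents.

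The documents do not support a claim of invalid inference, nor a claim that the allocation scheme itself is defective.

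**What to change.** **Section IV.E.** State that the main comparison of each one-month continuous score (knowledge, decisional conflict, self-efficacy) is a linear model with arm, the baseline value of that score, site and setting, reported as an adjusted difference with a 95% confidence interval. Report the t-test as a supporting analysis. List in advance any other covariates for the multivariate analysis. Make the change before outcomes are examined by arm.

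The cost is one sentence and four degrees of freedom (baseline 1, site 1, setting 2), leaving 120 − 6 = 114 against 118 for the t-test if all patients are followed. If the covariates predict nothing, the SE rises slightly: about 2.6% (0.198/0.193) in the simulation that adjusted for all six cells. No new data are needed.

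**Section IV.C.** State in the text whether the envelopes are stratified by site and setting, and whether they are blocked. Changing the scheme is optional. Separate envelope sets with small blocks would improve balance, but would make some assignments predictable to the coordinator who opens the envelopes. The analysis change is worth making either way.

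### The between-arm t-test for knowledge, decisional conflict and self-efficacy does not say score or change, and leaves the baseline score already collected unused

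*Combined protocol and SAP*

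**What the plan says.** Section IV.A, Aim 2, names three things the decision aid should change: "We are trying to determine if the decision aid improves hospice knowledge, decreases decisional conflict and improves self-efficacy".

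Section IV.C (Data collection) has all three measured at baseline: "All participants will be asked to complete the Hospice Knowledge Test, Decisional Conflict Scale, Decision Self-efficacy scale, SPMSQ, HADSA, PHQ-9 and demographics". Baseline collection comes before allocation is revealed; the next step begins "The research coordinator will then open the envelope to determine" the patient's arm. The same three scales are repeated at one month in both arms. The 1-week call is for the intervention arm only, so one month is the only follow-up at which the arms can be compared.

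Section IV.E (Quantitative Data) gives the comparison: "We will compare differences between intervention and control using t-tests for continuous outcomes and chi-square tests for dichotomous outcomes". It then adds a multivariate analysis of the same three outcomes, which will "look for mediation and/or moderation effects of age, race, and gender; while controlling for potential confounders". The confounders are not listed, the form of the model is not given, and the baseline score is not mentioned. Neither analysis is designated as the main estimate. The section also says there is no power calculation because this is a pilot.

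**The concern.** Two things are left unsettled.

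First, the t-test could be run on the one-month score or on change from baseline. Both are legitimate if chosen in advance. They give different estimates whenever the arms differ by chance at baseline, and the present wording would allow either to be reported.

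Second, neither t-test is generally the most precise use of the data. Regressing the one-month score on arm and baseline score is, in large samples, at least as precise as both, and the baseline score is already collected.

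The stake is modest but real. Section G makes a favourable early efficacy signal one condition, beside feasibility and acceptability, for moving to a multi-site trial. It names no scale, and efficacy is also assessed qualitatively. These three scales are nevertheless the quantitative part compared between arms at one month.

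**Working it through.** **Inputs from the document.** "We plan to recruit 120 patients" (IV.C, Settings) and "This will be a patient-level trial randomized in a 2:1 intervention: control" (IV.C, Research Methods) give 120 × 2/3 = 80 intervention and 120 × 1/3 = 40 control. The plan states no SD, correlation, dropout, significance level or power, so it has no figure to reproduce.

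**Assumed, not in the document.** Correlation ρ between baseline and one-month score of 0.3, 0.5 or 0.7; ratio k = baseline SD / one-month SD of 0.8, 1 or 1.25; no dropout, except in step 6; adjustment for baseline only. Results are in units of the one-month SD.

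**1. Score t-test.** Standard error = √(1/80 + 1/40) = 0.1936 SD. The 95% half-width is 1.98 × 0.1936 = 0.383 SD.

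**2. Variance relative to the score t-test.** Regression on baseline: 1 − ρ². Change-score t-test: 1 + k² − 2ρk.

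| ρ | Regression | Change, k = 0.8 | Change, k = 1 | Change, k = 1.25 |
|---|---|---|---|---|
| 0.3 | 0.91 | 1.16 | 1.40 | 1.81 |
| 0.5 | 0.75 | 0.84 | 1.00 | 1.31 |
| 0.7 | 0.51 | 0.52 | 0.60 | 0.81 |

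Multiplying the step 1 half-width by the square root of each ratio gives 0.366, 0.332 and 0.274 SD for regression at ρ = 0.3, 0.5 and 0.7. For change at k = 1 it gives 0.454, 0.383 and 0.297 SD. A simulation of 20,000 trials per case gave mean regression half-widths of 0.367, 0.333 and 0.274 SD, so estimating the baseline slope costs almost nothing at this size. At ρ = 0.5, adjustment is worth as much as raising the sample from 120 to 120/0.75 = 160.

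**3. Saving over a change-score t-test**, 1 − (1 − ρ²)/(1 + k² − 2ρk), at ρ = 0.3, 0.5 and 0.7:
- k = 0.8: 21.6%, 10.7%, 1.9%
- k = 1: 35%, 25%, 15%
- k = 1.25: 49.8%, 42.9%, 37.2%

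When k = ρ the two variances are equal and the saving is zero.

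**4. Gap between the two t-test estimates.** The score estimate minus the change estimate is exactly the baseline difference between arms. Its mean absolute size is k × 0.1936 × √(2/π): about 0.12, 0.15 and 0.19 SD at k = 0.8, 1 and 1.25.

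**5. Effect of leaving the choice open.** Suppose a two-sided 5% level were used and either test could be claimed. Under no effect the two estimates have correlation (1 − ρk)/√(1 + k² − 2ρk), for example 0.5 at k = 1 and ρ = 0.5. The bivariate normal probability that at least one test is significant is then 9.1%. Over all nine combinations it runs from 8.3% to 9.7% per scale.

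**6. With an assumed 25% loss (60 versus 30).** The score t-test half-width is 0.444 SD. With regression it is about 0.425, 0.386 and 0.318 SD (simulated).

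**The case against.** This is a pilot for feasibility and acceptability, with efficacy labelled preliminary and no power calculation. An unadjusted t-test is unbiased under randomisation, so preferring regression is close to taste. An adjusted analysis of the same three outcomes is already planned, and the baseline score may be among its unlisted confounders. The size of the gain rests wholly on assumed inputs and is negligible at ρ = 0.3. The 8% to 10% error rate supposes a 5% level and a selective choice of test, neither of which the plan describes. A smaller repair would do: state that the t-test uses the one-month score, and name baseline as a covariate in the multivariate analysis.

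Much of this stands. The t-test is valid and no stated power is missed. Baseline is not named rather than excluded, and the multivariate sentence covers the outcomes themselves as well as mediation and moderation. The error rate is conditional and shows only what the open choice could cost. The upper end of the range is also doubtful for knowledge. Section IV.A gives that scale an alpha of 0.75; if this approximates reliability at both visits, an observed correlation of 0.7 needs a true-score correlation of 0.7/0.75 = 0.93. The limit is weaker for self-efficacy, whose alpha is 0.92 (0.7/0.92 = 0.76).

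The remaining point is not answered. The smaller repair would still leave two arm estimates per scale, one from the t-test and one from the multivariate model, with neither named as the one to report.

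**Conclusion.** The concern holds as an improvement that should be made, not as a fault of validity. The score-or-change ambiguity and the absence of a named baseline covariate follow from the text alone. The precision gain over a score t-test is 9% to 49% of variance for correlations of 0.3 to 0.7. Over a change-score t-test it runs from nothing to about 50%, depending on the correlation and the SD ratio. These sizes depend on assumed correlations, SD ratios and retention. The conclusion is limited to the three scales listed for both arms at one month.

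**What to change.** In section IV.E, replace the t-test for these three outcomes with wording such as:

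> For hospice knowledge, decisional conflict and decision self-efficacy, the main efficacy estimate for each is the adjusted mean difference in the one-month score, intervention minus control, from a linear regression on randomised arm and the baseline value of that outcome, with a 95% CI.

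Label the mediation and moderation models exploratory, and list their covariates in place of the general reference to confounders. Adding site and care setting is optional unless randomisation was stratified by them; the text states no stratification. The wording gives one estimate per scale and does not rank the scales.

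The cost is a change of analysis-plan wording and one degree of freedom for the baseline term. No new data, patients or visits are needed.
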